## 6.5 Study Intervention Compliance

When participants are dosed at the site, they will receive the IP directly from the investigator or designee, under medical supervision. The dose of the IP and study participant identification at this time will be confirmed at the time of dosing by a member of the study site staff other than the person administering the study intervention.

When participants administer the IP at home, compliance with the IP will be assessed at each visit. Compliance will be assessed by inspecting the eDiary entries and returned supplies, with queries as necessary, during the site visits. Parent(s)/caregiver(s)/LAR(s) are to record daily seizure events in addition to study medication and non-study ASM administration in the eDiary device daily during the first year. Parent(s)/caregiver(s)/LAR(s) will be re-educated on the importance of adhering to daily seizure, IP and non-study ASM recording as needed. Deviation(s) from the prescribed dosage regimen should be recorded in the eCRF.

A record of the number of bottles of the IP dispensed to and taken by each participant must be maintained and reconciled with study intervention and compliance records. Intervention start and stop dates, including dates for intervention delays and/or dose reductions will also be recorded in the eCRF.

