# **7 DISCONTINUATION OF STUDY INTERVENTION AND PARTICIPANT DISCONTINUATION/WITHDRAWAL**

## **7.1 Discontinuation of Study Intervention**

In rare instances, it may be necessary for a participant to permanently discontinue study intervention. If the IP is discontinued at any time, participants should follow the 2-week taper schedule unless otherwise medically indicated such, as drug-induced rash. If the participant discontinues the IP, evaluations listed for the Early Termination Visit (Visit 13 [Week 156]; as shown in the SOA [Table 1]) are to be performed as completely as possible along with the end of study and safety follow-up assessment, as appropriate. Comments (spontaneous or elicited) or complaints made by the participant must be recorded in the source documents. The reason for termination, date of stopping IP, and total amount of IP taken must be recorded in the eCRF and source documents. Discontinuation of IP due to AEs must also be reflected on the AE eCRF page. Participants who discontinue IP should undergo a 2-week or shorter taper period, as clinically indicated. These participants will have a visit 2 weeks after the end of taper to complete the safety follow-up assessments.

The reason for early discontinuation of the IP must be determined by the investigator and recorded in the participant's source documents and on the eCRF. If a participant is withdrawn for more than 1 reason, each reason should be documented in the source document and the most clinically relevant reason should be entered on the eCRF.

Reasons for early termination include but are not limited to the following:

- AE (including pregnancy).
- Protocol violation/protocol deviation.
- Withdrawal by participant or parent(s)/LAR(s).
- Lost to follow-up.
- Lack of efficacy.
- Death.
- Investigator decision.

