### **8.4.1      Time Period and Frequency for Collecting Adverse Event and Serious Adverse Event Information**

All AEs are collected from the time of the first dose of the IP in the OLE until the defined follow-up period at the timepoints specified in the SOA (Section 1.3). Any AE that begins in a parent study and is ongoing at the time of the first dose of IP in the OLE will be included as an AE in the OLE. This includes events occurring during the initial visit in the study, regardless of whether or not the IP has been administered. All AEs reported after the initiation of IP will be considered treatment-emergent AEs. Where possible, a diagnosis rather than a list of symptoms should be recorded. If a diagnosis has not been made, then each symptom should be listed

individually. All AEs should be captured on the appropriate AE pages in the eCRF and in source documents. In addition to untoward AEs, unexpected benefits outside the IP indication should also be captured on the AE eCRF page.

Medical occurrences that begin before the start of study intervention but after obtaining informed consent will be recorded as medical history/current medical conditions, not as AEs.

All AEs must be followed to closure (the participant's health has returned to baseline status or all variables have returned to normal), regardless of whether the participant is still participating in the study. Closure indicates that an outcome is reached, stabilization is achieved (the investigator does not expect any further improvement or worsening of the event), or the event is otherwise explained. When appropriate, medical tests and examinations are performed so that resolution of event(s) can be documented.

All SAEs (regardless of relationship to study) are collected from the time the participant/parent(s)/LAR(s) signs the informed consent/assent until the defined follow-up period stated and must be reported to Marinus' drug safety vendor within 24 hours of the first awareness of the event.

In addition, any SAE considered "related" to the IP and discovered by the investigator at any interval after the study has completed must be reported to Marinus' drug safety vendor within 24 hours of the first awareness of the event.

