#### **8.4.7 Disease-related Events and/or Disease-related Outcomes Not Qualifying as Adverse Events or Serious Adverse Events**

Symptoms of the disease under study should not be classified as AEs as long as they are within the normal day-to-day fluctuation or expected progression of the disease. This includes seizures typical for that participant unless the seizures are changed in character, frequency, or duration. Significant worsening of the symptoms should be recorded as an AE.

The following disease-related events are common in participants with epilepsy and can be serious/life-threatening:

- Seizures.
- SE.

- Falls/trauma/accidents.

As these events are typically associated with the disease under study, they will not be reported according to the standard process for expedited reporting of SAEs even though the event may meet the definition of an SAE. These events will be recorded within 5 business days of when they are reported to the site. These disease-related events will be monitored on a routine basis.

Note: However, if either of the following applies, then the event must be recorded and reported as an AE/SAE (instead of a disease-related event):

- The event is, in the investigator's opinion, of greater intensity, frequency, or duration than expected for the individual participant, or
- The investigator considers that there is a reasonable possibility that the event was related to study intervention.

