### Events Meeting the AE Definition

- Any abnormal laboratory test results (hematology, clinical chemistry, or urinalysis) or other safety assessments (eg, 12-lead ECG, radiological scans, vital signs measurements), including those that worsen from baseline, considered clinically significant in the medical and scientific judgment of the investigator (ie, not related to progression of underlying disease).
- Exacerbation of a chronic or intermittent pre-existing condition including either an increase in frequency and/or intensity of the condition.
- New condition detected or diagnosed after study intervention administration even though it may have been present before the start of the study.
- Signs, symptoms, or the clinical sequelae of a suspected intervention-intervention interaction.
- Signs, symptoms, or the clinical sequelae of a suspected overdose of either study intervention or a concomitant medication. Overdose per se will not be reported as an AE/SAE unless it is an intentional overdose taken with possible suicidal/self-harming intent. Such overdoses should be reported regardless of sequelae.
- Lack of efficacy or failure of expected pharmacological action per se will not be reported as an AE or SAE. Such instances will be captured in the efficacy assessments. However, the signs, symptoms, and/or clinical sequelae resulting from lack of efficacy will be reported as AE or SAE if they fulfill the definition of an AE or SAE.
- The signs, symptoms, and/or clinical sequelae resulting from lack of efficacy will be reported as an AE or SAE if they fulfill the definition of an AE or SAE. Lack of efficacy or failure of expected pharmacological action also constitutes an AE or SAE.

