### Events NOT Meeting the AE Definition

- Any clinically significant abnormal laboratory findings or other abnormal safety assessments that are associated with the underlying disease, unless judged by the investigator to be more severe than expected for the participant's condition.
- The disease/disorder being studied or expected progression, signs, or symptoms of the disease/disorder being studied, unless more severe than expected for the participant's condition.
- Medical or surgical procedure (eg, endoscopy, appendectomy): the condition that leads to the procedure is the AE.
- Situations in which an untoward medical occurrence did not occur (social and/or convenience admission to a hospital).
- Anticipated day-to-day fluctuations of pre-existing disease(s) or condition(s) present or detected at the start of the study that do not worsen.

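### Withdrawals and dose reductions due to AEs are part of a primary endpoint, but the SAP text plans no table of AE-related dose reductions and at most a disposition count of AE withdrawals; the treatment-emergent and lack-of-efficacy rules also need reconciling

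*Protocol*

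**What the plan says.** **Endpoint and planned outputs.** Protocol 9.2.2 and SAP 2.3.1 both place withdrawals and dose reductions due to AEs in the first primary endpoint. Protocol 9.2.5 leaves detailed analyses and listings to the SAP. SAP 4.3.1 then lists ten tabular summaries and four separate listings. The only action with study drug that any of them names is interruption, which the summaries describe as interruption of an infusion. Protocol Table 2 describes an oral suspension taken three times a day.

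**Recording.** On withdrawal, Protocol 7.1 says that where there is more than one reason, "the most clinically relevant reason should be entered on the eCRF". It also says "Discontinuation of IP due to AEs must also be reflected on the AE eCRF page". Protocol 6.5 says "Intervention start and stop dates, including dates for intervention delays and/or dose reductions will also be recorded in the eCRF". Protocol 8.4.6, on deaths, refers to the IP action recorded for an event and gives interrupted, reduced and withdrawn as examples.

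**Treatment-emergent.** Under Protocol 8.4.1 a parent-study AE that "is ongoing at the time of the first dose of IP in the OLE will be included as an AE in the OLE". The same section treats every AE reported after IP initiation as treatment-emergent. SAP 4.3.1 requires onset or worsening on or after the first day of IP dosing. SAP section 6 declares no change from the protocol.

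**Lack of efficacy.** In Protocol 10.4.1 one bullet says "Lack of efficacy or failure of expected pharmacological action per se will not be reported as an AE or SAE". The next bullet ends with "Lack of efficacy or failure of expected pharmacological action also constitutes an AE or SAE".

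**The concern.** A primary endpoint component should have a named output in the SAP. Here the tolerability results that readers of a long-term safety extension look for, namely which AEs led participants to stop or reduce the drug, have no planned AE table. The infusion wording suggests text carried over from another study rather than a deliberate choice. So does a count of events of Grade 3 or higher, because Protocol 10.4.3 grades intensity only as mild, moderate or severe.

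The two definitional conflicts affect which events enter the AE tables at all. Participants enter the OLE already taking ganaxolone, including former placebo participants titrated before Study 1042-TSC-3001 ends (Protocol 1.1, Intervention Groups and Duration). An AE that began in parent-study titration and persists unchanged is therefore a realistic case. For lack of efficacy, sites following different bullets would record the same non-response differently. Under the second bullet, a withdrawal for lack of efficacy could also be counted as a withdrawal due to an AE.

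**Working it through.** The plan states no figure that depends on this point, so the check sets the texts side by side and counts planned outputs.

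**1. Outputs in SAP 4.3.1.** The ten summaries are: overall; by SOC/PT; by SOC/PT and maximum severity; related; by decreasing frequency; moderate or severe; moderate or severe and related; infusion interruption; serious; serious and related. Withdrawal or dose reduction appears in 0 of 10. The overall summary has six categories (any, related, serious, Grade 3 or higher, infusion interruption, death), and it appears in 0 of 6. The four separate listings cover all AEs, SAEs, interruptions and deaths, so neither action has a separate listing.

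**2. Cover elsewhere in the SAP.**

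| Component | Nearest output | What it gives | What it lacks |
|---|---|---|---|
| AE withdrawals | Disposition, SAP 5.4 | Count by reason for leaving the study | Which AEs and how severe; any AE that was not the one reason entered |
| AE dose reductions | Exposure listing, SAP 5.7 | Reason for each dose change, by participant | Any tabulation |

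**3. Whether the data exist.** Withdrawals due to AEs go on the AE page (Protocol 7.1). Protocol 6.5 supplies dates of dose reductions but no link to an AE. The link has to come from the action taken with IP per event, which Protocol 8.4.6 indicates is recorded. The eCRF itself is not among the documents.

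**4. Treatment-emergent rule.** Take an AE that began in the parent study, is unchanged at the first OLE dose, and is reported after IP initiation.
- Protocol 8.4.1: an OLE AE, and treatment-emergent.
- SAP 4.3.1, if the OLE dose is meant: not treatment-emergent, so absent from every TEAE table and shown only in listings.
- SAP 4.3.1, if the first ganaxolone dose in the parent study is meant: treatment-emergent if it began on or after that dose.

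The SAP does not say which dose applies. Its laboratory, vital-sign and ECG baselines (SAP 4.3.2 to 4.3.4) point to the OLE dose.

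**5. Lack of efficacy.** The two bullets cannot both be followed for bare non-response. For anything worse they do not matter. Protocol 8.4.7 says "Significant worsening of the symptoms should be recorded as an AE", and the list of events that are not AEs exempts only "expected progression, signs, or symptoms of the disease/disorder being studied, unless more severe than expected". Protocol 7.1 lists lack of efficacy and AE as separate termination reasons, which sits more easily with the first bullet. The SAP does not settle it.

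**The case against.** **The endpoint asks only for incidence of AE withdrawals, and the disposition table may supply that.** This stands in part. A reader might infer that AE withdrawals go unreported, and the documents do not support that: AE is one of the termination reasons in Protocol 7.1, and SAP 5.4 summarizes reasons. The SOC/PT format is a reviewer's recommendation and not a requirement of the endpoint wording. The objection does not reach dose reductions, which are only listed, and a count of one reason per participant can miss an AE that contributed.

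**The shells may contain the tables, and the all-AE listing may show action taken.** Both are possible; SAP sections 7 and 8 put these details in a separate document. It would go too far to infer that no listing will show these actions. The supported statement is that the SAP text names no separate listing and no table. An SAP should still name the outputs for its own primary endpoint.

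**The protocol does not make every carried-over AE treatment-emergent.** This is correct. Section 8.4.1 makes it an OLE AE; the treatment-emergent sentence covers AEs reported after IP initiation, and a carried-over AE may already have been reported in the parent study. The conflict is limited to those reported after initiation.

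**The lack-of-efficacy conflict is narrow.** This is also correct. A reader might infer that recording of seizure worsening is in doubt; step 5 of the working shows that it is not.

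**Conclusion.** The lead point holds on the SAP text: a named part of a primary endpoint has no tabulation of AE-related dose reductions and at most a disposition count of AE withdrawals. It should be fixed, and the repair is small. The treatment-emergent and lack-of-efficacy conflicts are real but secondary matters of wording.

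The size is unknown, because the documents give no OLE rate for AE withdrawals, AE dose reductions, carried-over AEs or bare non-response. Protocol 2.2.2.2 reports that 4 of 24 screened participants in Study 1042-TSC-2001 discontinued for AEs (4/24 = 16.7%). That shows only that the component need not be empty. It is not a forecast, since the denominator is screened participants and OLE entrants have already been taking ganaxolone. If no unworsened carried-over AE and no bare non-response is ever recorded, the two secondary conflicts change nothing.

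The other five primary safety endpoints are unaffected and all AEs remain listed. The study is descriptive (SAP 3.2), so a reader should not infer any effect on power or type I error. The conclusion assumes that the unseen shells do not already hold the tables.

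**What to change.** **SAP 4.3.1 (lead).** Replace the infusion-interruption items with summaries by SOC and PT of AEs leading to study drug interruption, to dose reduction and to withdrawal. Add the same three lines to the overall summary. Base them on the action taken with IP recorded per event, after confirming that field on the eCRF. Title them as AEs rather than TEAEs, so that AEs carried over from a parent study are included, with a label, when the action was taken in the OLE.

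**Treatment-emergent rule.** Keep the SAP's start-or-worsen rule and anchor it explicitly to the first OLE dose. Declare the difference from Protocol 8.4.1 in SAP section 6. Add a labelled SOC/PT table of AEs ongoing at OLE entry, so that AEs begun during ganaxolone titration in the parent study are not left in listings only.

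**Lack of efficacy.** Reconcile the two bullets in Protocol 10.4.1 at the next amendment. Meanwhile flag AEs recorded solely as lack of efficacy so that they can be shown separately.

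**Cost.** One SAP amendment before database lock. One action table becomes three and the entry table is added (2 + 1 = 3 net new tables); one overall-summary line becomes three; one data-review flag. No new data collection is expected if the action field is as Protocol 8.4.6 implies. The protocol wording needs IRB/IEC approval, and health authority approval if substantial (Protocol 10.1.1), across about 75 sites, but it can wait for the next planned amendment. Carried-over AEs may also appear in parent-study reports, so the label is needed to prevent double counting in pooled safety data.

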### Events NOT Meeting the AE Definition

- Any clinically significant abnormal laboratory findings or other abnormal safety assessments that are associated with the underlying disease, unless judged by the investigator to be more severe than expected for the participant's condition.
- The disease/disorder being studied or expected progression, signs, or symptoms of the disease/disorder being studied, unless more severe than expected for the participant's condition.
- Medical or surgical procedure (eg, endoscopy, appendectomy): the condition that leads to the procedure is the AE.
- Situations in which an untoward medical occurrence did not occur (social and/or convenience admission to a hospital).
- Anticipated day-to-day fluctuations of pre-existing disease(s) or condition(s) present or detected at the start of the study that do not worsen.

#### 10.4.2 Definition of SAE

An SAE is defined as any untoward medical occurrence that, at any dose, meets one or more of the criteria listed:

Results in death

Is life threatening
 
The term life threatening in the definition of serious refers to an event in which the participant was at risk of death at the time of the event. It does not refer to an event, which hypothetically might have caused death, if it were more severe.

Requires inpatient hospitalization or prolongation of existing hospitalization
 

• In general, hospitalization signifies that the participant has been admitted (usually involving at least an overnight stay) at the hospital or emergency ward for observation and/or treatment that would not have been appropriate in the physician's office or outpatient setting. Complications that occur during hospitalization are AEs. If a complication prolongs hospitalization or fulfills any other serious criteria, the event is serious. When in doubt as to whether hospitalization occurred or was necessary, the AE should be considered serious.

• Hospitalization for elective treatment of a pre-existing condition that did not worsen from baseline is not considered an AE.

Results in persistent or significant disability/incapacity
 

• The term disability means a substantial disruption of a person's ability to conduct normal life functions.

• This definition is not intended to include experiences of relatively minor medical significance such as uncomplicated headache, nausea, vomiting, diarrhea, influenza, and accidental trauma (eg, sprained ankle) that may interfere with or prevent everyday life functions but do not constitute a substantial disruption.

Is a congenital anomaly/birth defect

Is a suspected transmission of any infectious agent via an authorized medicinal product


Other situations:
 

• Medical or scientific judgment should be exercised by the investigator in deciding whether SAE reporting is appropriate in other situations such as significant medical events that may jeopardize the participant or may require medical or surgical intervention to prevent one of the other outcomes listed in the above definition. These events should usually be considered serious.

○ Examples of such events include invasive or malignant cancers, intensive treatment for allergic bronchospasm, blood dyscrasias, convulsions or development of intervention dependency or intervention abuse.

#### 10.4.3 Recording and Follow-up of AE and/or SAE

AE and SAE Recording

• The monitoring period for AEs begins at the time of the first dose of IP in the OLE.

• When an AE/SAE occurs, it is the responsibility of the investigator to review all documentation (eg, hospital progress notes, laboratory reports, and diagnostics reports) related to the event.

• The investigator will then record all relevant AE/SAE information.

• It is not acceptable for the investigator to send photocopies of the participant's medical records to IRB/IEC in lieu of completion of the required reporting forms.

• There may be instances when copies of medical records for certain cases are requested by IRB/IEC. In this case, all participant identifiers, with the exception of the participant number, will be redacted on the copies of the medical records before submission to IRB/IEC.

• The investigator will attempt to establish a diagnosis of the event based on signs, symptoms, and/or other clinical information. Whenever possible, the diagnosis (not the individual signs/symptoms) will be documented as the AE/SAE.

• Every reasonable effort will be made to follow up with participants who have AEs. Any participant who has an ongoing AE at the last study visit will be followed up, where possible, until resolution, or until the unresolved AE is judged by the investigator (or designee) to have stabilized. This will be completed at the investigator's discretion.

Assessment of Intensity

The investigator will make an assessment of intensity for each AE and SAE reported during the study and assign it to one of the following categories:
 

• Mild: Asymptomatic or mild symptoms; clinical or diagnostic observations only; intervention not indicated.

• Moderate: Minimal, local, or noninvasive intervention indicated; limiting age-appropriate instrumental activities of daily living (ADL). Instrumental ADL refers to preparing meals, shopping for groceries or clothes, using the telephone, managing money, etc.

• Severe: Severe or medically significant but not immediately life-threatening; hospitalization or prolongation of hospitalization indicated; disabling, limiting self-care ADL. Self-care ADL refers to bathing, dressing, and undressing, feeding self, using the toilet, taking medications, and not bedridden.

